Patient data collected by Cegedim in each country participating in the LPD varies to some extent to accommodate local needs. However, all countries collect data on medical comorbidities and outcomes, prescriptions, demographics, and physician characteristics.

In the Cegedim electronic medical record system diagnosis of clinical events are recorded as diagnostic codes. These codes from the different participating countries will be harmonized based on pre-specified algorithms developed prior to the analysis and listed in the statistical analytic plan.

Cegedim LPD does not collect hospitalization data directly in Italy and Spain. Information on hospitalizations is captured in the patient's general practice file during follow-up visits with the patient's general practice physician following discharge from the hospital. However, this information is not systematically collected and there is no established linkage between the medical records at the general practices and at the hospitals.

Table 2: Data coding conventions in the different countries

	Italy	Spain
Drug code dictionary	Farmadati	Vademecum
Therapy classification	Anatomical Therapeutic Chemical (ATC)	ATC
Disease classification	ICD-9	Code ICPC mapped to ICD-9

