7 HANDLING OF MISSING VALUES

For each variable, the number and proportion of patients missing data for each treatment group will be specified. The primary analyses will be done using only the information available in the unmodified dataset. Smoking status, alcohol consumption, height and/or weight (BMI) values are known to be missing for approximately 40-60% patients in the Cegedim LPD based on previous studies. (Age of patients will always be known as it is a selection criterion). Dates are automatically recorded in the Cegedim LPD and doctors can select diseases codes from the pre-defined lists. In all analyses, if a condition (disease or treatment) other than the diagnosis of osteoporosis is not recorded, it will be assumed to be non-existent.

To estimate the effect of missing data, two additional analyses for the primary study endpoint will be conducted. First, the analyses will be repeated utilizing a dataset in which cases with missing values of main study covariates of BMI, smoking status and alcohol status are excluded. The disadvantage to this approach is the reduction in the sample size. Another disadvantage to this approach is that the subjects with missing values may be different than the subjects without missing values (e.g., missing values that are not missing at random), resulting in a non-representative sample after removing the cases with missing values. Second, multiple imputations for the missing values of BMI, smoking status, alcohol status will be used in the second set of analyses and compared to complete case analyses to understand the potential impact of missing data on results [2].

Outlier

Extreme values for weight and height will be searched for. If a value seems implausible, as regard to gender or ratio weight/height, it will be put as missing.

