8.1.3 SENSITIVITY ANALYSIS

For each prescription, duration of drug exposure will begin to accrue from the date of the prescription. The duration of drug exposure will be categorized into:

- ***Current exposure:*** defined as the duration of the prescription
- ***Recent exposure:*** defined as the 60-day period following the end of the duration of prescription
- ***Past exposure:*** defined as any follow up time accrued after 60 days following the end of the duration of the prescription.

Given the discontinuous nature of osteoporosis medication use, it is likely that a large number of women in this study will accrue 'current exposure', 'recent exposure' and 'past exposure' exposure time to multiple osteoporosis drugs during the 5-year period of follow up.

A sensitivity analysis will be conducted that compares using a 30-day and a 90-day definition of recent exposure with using the 60-day definition.

Exposure to the drugs under study will be ascertained by searching the prescription records for the relevant product codes. For each prescription the duration of exposure will be estimated based on the dose and quantity of the prescribed medication. For patients that switch treatment, the as-treated (AT) approach will be used in calculating the exposure time (see section below on patients switching treatment for more details).

There will be rules for handling missing values of dose or quantity prescribed in Italian and Spanish LPD databases. In LPD databases, the number of days of supply or daily

dose is not recorded by some GPs in Spain and Italy. If duration is not available, the number of days of supply will be calculated by dividing total number of pills (number of prescribed box times number of pills in a box) by the daily dose. If duration and daily dose are not available, the number of days' supply will be calculated by dividing total number of pills (number of prescribed box multiplied by the number of pills in a box) by the standard dose/recommended dose.

Drug exposure will also be categorized with respect to the cumulative exposure to each drug (e.g., 0-days, 1-30-days, 31-90-days, 91-180-days, 181-365-days, >365-days) to evaluate whether or not the incidence (hazard) of a specific adverse event varies with increased duration of use.

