In the treatment of chronic conditions such as osteoporosis, patients may discontinue their study medication (BZA/bisphosphonate/raloxifene) or change study medications. Such exposure changes are often due to treatment failure or perceived/real side effects. The stronger such non-adherence is associated with the outcome; the more an as-treated (AT) analysis, which censors at the point of discontinuation, will be biased. A cumulative risk (CR) (similar to intention-to-treat analyses in randomized trials) analysis follows all patients for a fixed time period, carrying forward the initial exposure status and disregarding any changes in treatment status over time. Because this analysis disregards informative non-adherence, it will not suffer bias as a consequence of censoring, but it will suffer bias as a consequence of exposure misclassification. Such misclassification increases with a longer follow-up period and a shorter average time to discontinuation. In most cases, though not all, such misclassification will bias effects towards the null, similar to intention-to-treat analyses in randomized trials. Viewed separately, the AT and CR analyses trade biases, but together they give a range of plausible effect estimates. Adjusting for non-adherence in an analysis of a drug effect requires information about the predictors of treatment discontinuation, which is not available with sufficient accuracy in secondary data such as that used in this study [1].

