In this study the proportion and demographic and clinical characteristics of patients that switch medications between the study drugs will be reported alongside patients that do not switch medications. Both the AT and CR analytic approaches will be used for all study endpoints and the results reported. In the CR method, if a patient switches from one exposure (study drug) cohort group to another, they will have several treatment durations and will belong to multiple cohort groups but will be analyzed according to their original exposure cohort group (i.e., CR/intent to treat approach). In the AT approach, all exposure cohort groups will be included as a time-dependent variable. With the exposure cohort group as a time-dependent variable, each event will be assigned to the treatment being taken at the time of occurrence. The duration of treatment for each cohort group will be from the date of the first prescription to the date of the event or to the end of treatment, whichever occurs first. The covariates of patients that switched treatment at the time of the event or at the end of follow-up would be considered in this model.

[figure not shown]
The following diagrams shows some example of calculating duration for patients with switched treatments with both the AT and CR approaches.

Figure 2a. Calculating the duration of treatment for patients that switched treatment using the as-treated (AT) approach.

A, B, C: Treatment cohort types. X= Incidence date of primary end point

Figure 2b. Calculating the duration of treatment for patients that switched treatments using the cumulative risk (CR) approach.

A, B, C: Treatment cohort types. X= Incidence date of primary end point

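### The as-treated rule has no carry-over, switch-day or event-dating provision, so a VTE that reaches the GP file after bazedoxifene has ended can be lost or credited to the next drug

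*SAP*

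**What the plan says.** SAP 8.1.4, under Patients Switching Medications, makes the drug group a time-dependent variable in the as-treated (AT) analysis. It says that "each event will be assigned to the treatment being taken at the time of occurrence", and that time on each drug runs from its first prescription "to the date of the event or to the end of treatment, whichever occurs first". It gives no carry-over period and no rule for an event dated on the day of a switch. On why women change drug, it says: "Such exposure changes are often due to treatment failure or perceived/real side effects". The companion cumulative-risk (CR) analysis keeps each woman in her original group.

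On how events reach the data, SAP 2.1 (and Protocol 3.2) says that hospital information is "captured in the patient's general practice file during follow-up visits with the patient's general practice physician following discharge from the hospital", that it is not collected systematically, and that there is no linkage to hospital records. SAP 8.1.2 ends person-time at the date of diagnosis of the endpoint. SAP 7 adds: "Dates are automatically recorded in the Cegedim LPD". Protocol 6.3 has a clinical expert review the record of each potential VTE, but only to confirm the diagnosis.

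SAP 8.1.3 sets exposure from the dose and quantity prescribed. It splits follow-up into current, recent and past exposure, with recent "defined as the 60-day period following the end of the duration of prescription", and varies that window to 30 and 90 days. For women who switch, it refers to the AT rule.

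**The concern.** Suppose a woman has a VTE while on BZA and is admitted. The GP enters the event at a later visit, by which time her BZA supply has run out or another osteoporosis drug has been prescribed. If the event carries the date of entry, the AT rule places it in unexposed time or in the new drug's time. The recent-exposure category could catch it, but SAP 8.1.4 does not say that recent exposure counts as exposed in the AT model.

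The direction matters in a safety study. Protocol 1.1 and the SAP introduction state that VTE is in the BZA label as an identified risk. A drug change after a VTE is therefore plausibly more common on BZA than on a bisphosphonate, which would lower the AT hazard ratio for BZA. SAP 8.1.4 does warn that "an as-treated (AT) analysis, which censors at the point of discontinuation, will be biased" when non-adherence is associated with the outcome. That warning is about informative stopping. Late entry of an event that happened on drug is a separate error, and the SAP does not discuss it.

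**Working it through.** **Inputs.** VTE rate without a SERM or hormone therapy: 1.74 per 1000 patient-years (Protocol 7.1). True ratio: 2, one of the values in Protocol Table 3. Groups: 1,823 BZA and 10,938 bisphosphonate women, 1:6 (SAP 5.4). Interval: Wald 95% on the log rate ratio, IRR × exp(±1.96 × √(1/a + 1/b)), where a and b are the BZA and bisphosphonate event counts.

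**Reproducing the plan's figure.** Take 5 × 0.85 = 4.25 patient-years per woman, that is, the 15% loss applied once. For the 1,750 : 10,500 row at a ratio of 2:
- a = 1,750 × 4.25 × 0.00348 = 25.9
- b = 10,500 × 4.25 × 0.00174 = 77.6
- interval 1.28 to 3.12, against 1.3 to 3.1 in Table 3.

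**Effect on the ratio.** Let f be the share of BZA VTEs dated after BZA time ended. The documents give no value, so f is an assumption. No bisphosphonate event is misdated here. At a true ratio of 2 with 1:6 groups, b = 3a before any misdating.
- Lost: ratio = 2(1 − f).
- Credited to the bisphosphonate: ratio = 2(1 − f) / (1 + f/3).

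| f | Lost | Credited |
|---|---|---|
| 10% | 1.80 | 1.80 / 1.033 = 1.74 |
| 25% | 1.50 | 1.50 / 1.083 = 1.38 |

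These ratios do not depend on the patient-years assumed. The intervals do.

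**Intervals with the SAP's group sizes at 4.25 patient-years.** a = 1,823 × 4.25 × 0.00348 = 27.0 and b = 10,938 × 4.25 × 0.00174 = 80.9; with nothing misdated the interval is 1.29 to 3.09.
- f = 10%: lost 1.14 to 2.83; credited 1.11 to 2.74.
- f = 25%: lost 0.92 to 2.44; credited 0.85 to 2.25.
- The lower limit reaches 1 at f = 19.7% lost (27.0 × 0.197 = 5.3 events) or f = 16.3% credited (27.0 × 0.163 = 4.4 events).

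**With less time on drug.** The AT analysis counts treated time only, which may be well short of 4.25 years. Assuming 2 on-drug years per woman, a = 12.7 and b = 38.1. The interval starts at 1.06 to 3.78, and losing a single BZA event takes the lower limit to 0.96.

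**Same share misdated in both arms (4.25 patient-years).** If all such events are unassigned, the ratio stays at 2.00, and at f = 10% the interval only widens, to 1.26 to 3.17. If the BZA events cross to the bisphosphonate while the bisphosphonate events are unassigned, the ratio at f = 10% is 6 × 24.3 / (72.8 + 2.7) = 1.93. Bias therefore needs a differential share or events crossing arms.

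**The case against.** Several points on the other side stand.

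- **Event date.** A reader might infer that the SAP assigns VTEs by the date of GP entry. It does not say so. The AT rule refers to the time of occurrence, the legends of Figures 2a and 2b refer to the incidence date, and SAP 2.1 lists event dates among the data collected. The remark on automatic dates sits in the missing-data section. Some hospital VTEs may carry their true date; the gap is that no rule ensures it.
- **Same-visit switch.** A reader might also infer that a VTE entered at the visit where a new drug is prescribed must go to the new drug. The SAP has no tie rule, and the usual start-stop coding of a time-dependent exposure would leave that event with the earlier drug.
- **Supply.** Exposure is built from prescriptions, so BZA time can run to the end of supply even if she stopped earlier. A short delay in recording may still fall in BZA time.
- **Role of AT.** SAP 8.1.2 makes cumulative incidence the primary approach, SAP 8.2.4 calls time-to-event analysis secondary, and AT is one of two versions reported. CR cannot credit an event to a later drug.
- **Both ends too low.** It is tempting to conclude that AT and CR must both understate the risk. The SAP says only that CR misclassification biases toward the null in most cases, and the AT bias is conditional.

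Figure 2a is not available in the text reviewed, so its treatment of gaps could not be checked. None of these points supplies the missing dating, tie or carry-over rule.

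**Conclusion.** The concern holds as a gap in the AT specification. As written, a BZA VTE dated after supply ended or after a switch can be lost or credited to the next drug, and neither the 60-day recent category nor the record review is tied to the AT rule. Downward bias in the AT hazard ratio is plausible but conditional on differential misdating or on events crossing arms.

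The size is illustrative. It rests on a true ratio of 2, on assumed shares of 10% and 25%, and on no misdating of bisphosphonate events. With about 27 BZA VTEs expected at 4.25 patient-years, about five lost or four credited would bring the lower limit to 1. With fewer on-drug years it takes fewer. The documents do not support a claim that the study as a whole will understate the VTE risk of BZA: its primary incidence analysis and the CR analysis do not use this rule. The gap should be closed before the final analysis because the AT estimate is one end of the range the SAP offers for this identified risk.

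**What to change.** In SAP 8.1.4:

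1. Define the VTE date: the admission or onset date where the record review in Protocol 6.3 shows one, otherwise the entry date.
2. Assign a VTE dated on the day of a switch to the drug being stopped.
3. For women who stop without starting another study drug, run the AT analysis with a current-plus-recent risk window: end of supply plus the 60 days of SAP 8.1.3, with 30 and 90 days as sensitivity analyses. Report it beside the existing AT version.
4. For VTEs within 60 days after a switch, report results with the event assigned to the new drug and, as a sensitivity analysis, to the earlier drug.

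Reassignment to the earlier drug should not be the main rule. BZA was launched after the bisphosphonates, so switches from a bisphosphonate to BZA are plausible. Reassignment would then credit early BZA events to the bisphosphonate and again lower the BZA ratio.

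The cost is SAP wording, some reprogramming of the exposure variable and one more item for the record reviewer to note; no new data are needed. The wider window counts some off-drug time as exposed, which slightly dilutes the estimate; the 30-day window and the existing AT version show by how much.

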##### **6.1.2. Drug exposure:**

Exposure to the drugs under study will be ascertained by searching the prescription records for the relevant product codes. For each prescription the duration of exposure will be

estimated based on the dose and quantity of the prescribed medication. For each prescription, person-time exposed to the drug will begin to accrue from the date of the prescription. The follow up time will be categorized into:

- **Current exposure:** defined as the duration of the prescription
- **Recent exposure:** defined as the 60-day period following the end of the duration of prescription
- **Past exposure:** defined as any follow up time accrued after 60 days following the end of the duration of the prescription.

A sensitivity analysis will be conducted with a different definition of exposure categories (e.g., using a 90-day window to define recent exposure).

Given the discontinuous nature of osteoporosis medication use, it is likely that a large number of women in this study will accrue ‘current use’, ‘recent use’ and ‘past use’ exposure time to multiple osteoporosis drugs during the 5-year period of follow up.

Drug exposure will also be categorized with respect to the cumulative exposure to each drug (e.g., 0-days, 1-30-days, 31-90-days, 91-180-days, 181-365-days, >365-days) to evaluate whether or not the incidence (hazard) of a specific adverse event varies with increased duration of use.

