8.1.1 PATIENT CHARACTERISTICS

The following characteristics will be reported for all treatment cohorts at baseline.

- Demographic Characteristics: Age, BMI, Smoking

Age (years) at index date will be calculated as Age = year (index date)-year (birth).

Four age groups are defined (in years): 45-49, 50-59, 60-69 and 70 and over.

BMI (Body Mass Index) will be calculated for each patient as the weight in kg divided by square of height in meters. BMI will be calculated using the following formulas:

$$BMI (kg/m^2) = Weight (kg) / (Height (m))^2$$

Or

$$BMI (kg/m^2) = 10000 \times Weight (kg) / (Height (cm))^2$$

- BMI will be categorized into four groups as follows:
- Underweight: BMI <18.5 kg/m²
 - Normal range: 18.5 ≤ BMI <25 kg/m²
 - Overweight: 25 ≤ BMI <30 kg/m²
 - Obese : BMI ≥30 kg/m²
- Smoking will be defined as three categories; Current Smokers, Former Smokers and Never Smokers. A 'Current Smoker' will be defined as a patient who is currently smoking at the index prescription date, a 'Former Smoker' as a patient that has a past history of smoking but has stopped prior to the index prescription date. A 'Never Smoker' will be defined as a patient that has no history of smoking (The reported frequency of smoking may be very low because smoking status is under recorded in Italian and Spain databases)
 - Alcohol use. Alcohol use will be defined as three categories; Current Drinkers, Former Drinkers and Never Drinkers. A 'Current Drinker' will be defined as a patient who is currently drinking alcohol as at the index prescription date, a 'Former Smoker' as a patient that has a past history of drinking alcohol but has stopped drinking prior to the index prescription date. A 'Never Drinker' will be defined as a patient that has no history of drinking alcohol. (The reported frequency of alcohol use may be very low because alcohol use is under recorded in Italian and Spain databases).
 - Use of relevant concomitant medications, e.g., hormone replacement therapy. (A concomitant medication is any medication used during BZA/bisphosphonate/raloxifene treatment defined as the total treatment duration between the first and the last prescription of BZA/bisphosphonate/raloxifene.)
 - Medical History VTE (Venous Thromboembolic Events), Diabetes, Hypertension, and Malignancies (including Breast, Renal, Thyroid, Ovarian, Gastrointestinal tract, Lung) and aggregate of all malignancies.

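### The as-treated person-time rule in SAP 8.1.4 leaves end of treatment undefined and, read literally, puts off-drug days into a drug's exposed time

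*SAP*

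**What the plan says.** The part of SAP 8.1.4 on patients switching medications makes four statements about AT:

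- Exposure coding: "In the AT approach, all exposure cohort groups will be included as a time-dependent variable".
- Events: "each event will be assigned to the treatment being taken at the time of occurrence".
- Time for each cohort group: "from the date of the first prescription to the date of the event or to the end of treatment, whichever occurs first".
- In the paragraph before, AT is described as an analysis "which censors at the point of discontinuation".

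End of treatment is not defined. Figure 2a, which illustrates AT durations for switchers, is not visible in the text available for review.

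Elsewhere exposure is built from individual prescriptions. Protocol 6.1.2 has "For each prescription, person-time exposed to the drug will begin to accrue from the date of the prescription", and SAP 8.1.3 has "For each prescription, duration of drug exposure will begin to accrue from the date of the prescription". Both then divide time into current, recent (60 days after supply ends) and past. For switchers, however, SAP 8.1.3 says exposure time follows the AT approach and refers the reader to the switching section. The same section expects many women to have interrupted use of several drugs: "Given the discontinuous nature of osteoporosis medication use".

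**The concern.** Three rules are in play: a span per drug, censoring at discontinuation, and accrual per prescription. They give different person-time for any woman who stops and restarts or who returns to an earlier drug, and the plan expects many such women. SAP 8.1.3 does not clearly settle the matter, because for switchers it points back to the section that contains the span.

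Taken at its word, the span credits a drug with days on which it was not prescribed. SAP 8.1.4 presents AT and the cumulative-risk (CR) analysis as a pair whose different biases bracket the plausible effect, and it says that misclassification in CR usually pulls towards the null. If AT also absorbs off-drug time, both analyses can lean the same way and the bracket may miss the true effect. The endpoint at stake is VTE, which is the primary endpoint and an identified risk of BZA.

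**Working it through.** The plan states no AT rate or coverage, so there is no figure to reproduce. The check compares the three rules on one history and then works out the dilution.

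**1. One assumed history under each rule.** Drug A for 365 days, gap of 180, drug B for 365, drug A again for 365. Calendar time is 365 + 180 + 365 + 365 = 1275 days.

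| Rule | Days credited to A | Days credited to B |
|---|---|---|
| Literal span, first prescription to final end of A | 1275 | 365 |
| Censoring at first discontinuation | 365 | 0 |
| Prescription by prescription | 730 | 365 (gap of 180: 60 recent, 120 past) |

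Under the span, 730 / 1275 = 57% of A's time is on A. A rate that counts only on-A events is then 43% too low. In a rate table the two drugs together receive 1275 + 365 = 1640 days out of 1275.

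**2. Inputs for the dilution.** The VTE rate without a SERM is 1.74 per 1000 PY (Protocol 7.1). It is used here for bisphosphonate users and, by assumption, for gap time. The illustrative true ratio is 2, one of the values in Protocol Table 3, so the on-drug BZA rate is 2 × 1.74 = 3.48. Let c be the share of a drug's span covered by its prescriptions. The documents do not give c, so a range is shown.

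**3. Gap days and gap events both carry the drug label.** This can happen in the time-dependent Cox model, because the stated variable consists of the cohort groups and names no unexposed state. With constant hazards and background risk in gaps:

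reported ratio = 1 + c(BZA) × (true ratio − 1)

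| c(BZA) | Reported ratio (true 2.0) |
|---|---|
| 1.0 | 2.0 |
| 0.8 | 1.8 |
| 0.6 | 1.6 |
| 0.5 | 1.5 |

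At c = 0.6 the BZA rate is 0.6 × 3.48 + 0.4 × 1.74 = 2.78, and 2.78 / 1.74 = 1.6. Bisphosphonate coverage does not enter, because that rate is assumed to be the same on and off drug.

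**4. Rate tables with on-drug events over span time.** Here reported rate = on-drug rate × c, so c = 0.9, 0.8 or 0.5 lowers a rate by 10%, 20% or 50%. The reported ratio is the true ratio × c(BZA) / c(bisphosphonate).

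| c BZA / c bisphosphonate | BZA rate | Bisphosphonate rate | Ratio |
|---|---|---|---|
| 0.8 / 0.8 | 2.78 | 1.39 | 2.00 |
| 0.6 / 0.6 | 2.09 | 1.04 | 2.00 |
| 0.6 / 0.8 | 2.09 | 1.39 | 1.50 |
| 0.8 / 0.6 | 2.78 | 1.04 | 2.67 |

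With time restricted to on-drug days, the rates return to 3.48 and 1.74 and the ratio to 2.00.

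**The case against.** The strongest reply is that the span is only one reading. A single time-dependent exposure variable has one value on any day, so a B spell between two A spells is coded B in the Cox model. Censoring at discontinuation would keep later gaps out altogether. SAP 8.1.3 accrues time per prescription, and Figure 2a may show separate spells. All of this stands as far as intent goes, and it rules out double counting of B time in the Cox hazard ratio. It does not say what happens to gap days or which of the conflicting rules governs.

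A reader might also infer that a VTE in a gap counts for no drug. The SAP does not say so; it has no rule for such an event. That is why steps 3 and 4 are shown as alternatives. Nor does step 4 carry over to the planned drug comparison, which is the Cox hazard ratio (SAP 4.2), where events and risk sets share one coding.

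The first-to-last-prescription period in SAP 8.1.1, "defined as the total treatment duration between the first and the last prescription of" the study drugs, might be read as confirming the span. It serves to define concomitant medication and is not an AT rule.

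Finally, AT is neither the primary analysis nor the only one that separates on-drug from off-drug time. SAP 8.1.2 makes cumulative incidence primary and uses ever-exposed person-time, SAP 8.2.4 makes time-to-event secondary, SAP 8.1.3 has its own exposure categories, and CR does not use this rule. This limits the reach of the problem but leaves AT, which is planned for every endpoint, without a workable definition.

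**Conclusion.** The point holds as an inconsistency that should be corrected before the AT analysis is run. It is more than missing detail, because following the one sentence that sets AT duration puts off-drug days into exposed time.

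The size depends on coverage, which the documents do not give. If gap time and gap events carry the BZA label, a true hazard ratio of 2.0 against bisphosphonate falls to between 1.8 and 1.5 for assumed BZA coverage of 0.8 to 0.5, and to 1.6 at 0.6. This rests on constant hazards and on risk returning to background once supply ends; any lingering effect would make the dilution smaller. In rate tables with on-drug events only, each rate falls in proportion to coverage, and the ratio shifts only when coverage differs, in either direction.

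The tempting stronger conclusion is that the plan necessarily understates a BZA excess. The documents do not support it: nothing in them shows longer gaps on BZA, the span is the literal reading and not proven intent, and Figure 2a could not be checked.

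**What to change.** In SAP 8.1.4, replace the span sentence with a rule along these lines: the AT analysis uses the prescription-based states of SAP 8.1.3 as the time-dependent exposure, namely current, recent (60-day window, with the planned 30- and 90-day sensitivity analyses) and past or not currently exposed, for each drug. The rule should also say that:

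- each spell starts and stops separately;
- time on an intervening drug is coded to the drug being taken;
- the same day-level coding applies to events and to person-time, including those in gaps;
- end of treatment is defined accordingly.

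Add a rule for days on which prescriptions for two drugs overlap. Bring the description of AT as censoring at discontinuation, and Figure 2a if it shows a single span, into line. Keeping recent as its own state means that a refill a few days late is not treated as past exposure.

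The cost is SAP wording and some programming, since SAP 8.1.3 already derives the prescription durations. There will be fewer AT person-years, so AT intervals will be slightly wider.
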